6.3. Handling of Dropouts or Missing Data

The analyses of the primary and multiplicity adjusted objectives will be performed for the ITT estimand and the efficacy estimand. The ITT estimand includes all data collected through Week 16 regardless of IP use and the efficacy estimand includes data collected prior to permanent discontinuation of IP through Week 16. The analyses of the multiplicity adjusted CGM endpoints for the efficacy estimand will also exclude data that are collected while patients are temporarily off pump or off study treatment.

For the Food and Drug Administration (FDA) submission, the ITT estimand will be used and the imputation of missing data for HbA1c will be performed as described in Section 6.11.1.

For the non-FDA submissions, the efficacy estimand will be used. Missing data will be addressed by using a mixed-effect model repeated measures (MMRM) analysis for continuous longitudinal variables. The MMRM model provides consistent estimator when data is missing at random. The model implicitly adjusts for missing data through a variance-covariance structure. An analysis of covariance (ANCOVA) model will also be used to analyze continuous variables. For the ANCOVA model, unless otherwise stated, missing endpoints will be imputed using the last-observation-carried-forward (LOCF) approach, using only postbaseline data.

6.4. Multicenter Studies

Countries in similar geographic regions with fewer than 10 patients, based on the all-randomized population, will be pooled to achieve a pooled country of at least 10 patients. All analyses using country in the model will use a pooled country, unless otherwise specified. The final pooling by country and geographic region will be finalized prior to data lock.

6.5. Multiple Comparisons/Multiplicity

A graphical approach for multiple comparisons (Bretz et al. 2011) will be used to strongly control the overall Type I error (2-sided alpha level of 0.05) for testing the treatment effect for the primary and multiplicity adjusted objectives listed in Section 4. See Section 6.11.2 for the details of graphical testing scheme.

No multiplicity test adjustment will be made for other objectives.

6.6. Patient Disposition

Patient disposition will be displayed in a flowchart showing the number of patients entered, enrolled, randomized, and discontinued across all study periods.

Frequency counts and percentages of all randomized patients completing and discontinuing from the study will be presented for each treatment group. Reasons for discontinuation from the study and study treatment will be compared between treatment groups using Fisher's exact test.

Frequency counts and percentages of all patients entered, enrolled, and discontinued from the study during the lead-in period will be summarized. Reasons for discontinuation during screening will be summarized for all entered patients. Reasons for discontinuation from the study during the lead-in period will be summarized for all enrolled patients.

A listing of the primary reason for treatment discontinuation (if applicable) and study discontinuation will be generated for the Randomized Population.

Patient allocation by investigator, grouped by country, will be summarized indicating the number of patients who enter the study, the number of patients who participate in the lead-in period, the number of patients who are randomized to study treatment, and the number of patients who discontinue the study during the 16-Week treatment period.

A listing of the randomization treatment assignment will be generated for all randomized patients.

6.7. Patient Characteristics

A summary table will be generated for patient and diabetes characteristics at study entry using all randomized patients. The following variables will be included but not limited to: age, age groups (<40 and \geq 40 years, and <65 , ≥ 65 to <75 , ≥ 75 to <85 , ≥ 85 years), sex, country, ethnicity, race, height, weight, body mass index (BMI), BMI group (<25 , ≥ 25 to <30 , ≥ 30 kg/m²), duration of diabetes, duration of CSII use, insulin pump brand and model, infusion set model, the type of rapid-acting insulin at study entry, total daily dose at study entry, patient's personal CGM or

FGM use during the study (each separately and combined as stratification factor), bolus speed, use of low glucose suspend during the study, HbA1c at study entry and baseline, and HbA1c stratum (based on measurement at baseline).

For continuous variables, the following statistics will be provided: mean, SD, minimum, maximum, and median, and treatment groups will be compared using an ANOVA model with a term of treatment. For categorical variables, summary statistics will include sample size, frequency and percentage, and treatment groups will be compared using Fisher's exact test or Pearson's chi-square test. A listing of patient characteristics at study entry will be provided.

A listing of patients whose stratification factor value entered into the IWRS (for treatment group assignment) is different from the clinical database will also be provided.

For all randomized patients, the number and percentage of patients with historical conditions will be summarized by treatment group using Medical Dictionary for Regulatory Activities (MedDRA) preferred term (PT) nested within system organ class (SOC), and the number and percentage of patients with preexisting conditions will also be summarized by treatment group using MedDRA PT nested within SOC. Historical conditions are conditions that end prior to inform consent and preexisting conditions are conditions that are still ongoing at inform consent. Events will be ordered by decreasing frequency. No statistical comparisons between treatment groups will be performed.

6.8. Treatment Compliance

No analysis for treatment compliance is planned for this study.

6.9. Important Protocol Deviation

Important protocol deviations (IPD) that potentially compromise data integrity or patients' safety will be summarized by treatment group for all randomized patients. The listing of important protocol deviations for all randomized patients during the entire study will be provided in the CSR. The IPDs identified by site monitoring and clinical database will be integrated in the listing. If the IPD is identified by both methods, only the site monitoring IPD will be presented.

6.10. Concomitant and Prior Therapy

Concomitant medication will be summarized and compared between treatment groups using Fisher's exact test for the Randomized Population during the treatment periods (0 to 16 weeks). The percentages of patients receiving each concomitant medication will be summarized by treatment using PT nested within Anatomical Therapeutic Chemical (ATC) Level 3 code. Medications will be ordered by decreasing frequency within ATC level. Concomitant medication used during the lead-in period will also be summarized for the Enrolled Population.

A summary of previous diabetes therapies that were discontinued prior to informed consent will be generated for the Enrolled Population.

The daily basal dose, daily bolus dose, total insulin dose, and the ratio of bolus dose to total insulin dose during the lead-in period will be summarized by visit for each treatment. The doses

and bolus/total insulin dose ratios for each visit will be calculated as the mean of the doses for the last 3 days prior to the visit date that are entered in the eCRF. Doses will be summarized in U and U/kg.

6.11. Efficacy Analyses

6.11.1. Analysis of Primary Objective

The primary objective of this study is to test the hypothesis that LY900014 is noninferior to Humalog on glycemic control (NIM = 0.4% for HbA1c) in patients with T1D using CSII with bolus doses delivered 0 to 2 minutes prior to the meal for 16 weeks. There will be 2 primary analysis methods, each tested at the full significance level of 0.05.

For the United States (US) FDA submission, the primary analysis method will use the copy reference approach to impute missing data based on multiple imputations with a pattern mixture model. This analysis is for the ITT estimand that will include all data collected from randomization through Week 16, regardless of IP use. The reference will be all observed data from the randomized patients in the same treatment group who discontinue IP and complete the study without missing data. After imputation, the primary efficacy comparison will be based on the contrast between LY900014 and Humalog from an ANCOVA model. The model for the change from baseline to the Week 16 HbA1c endpoint will include treatment and strata (country and patient's personal CGM or FGM use during the study) as fixed effects and baseline HbA1c as a covariate.

If there are only a limited number of patients in the reference group as described above that leads to a failure in performing the proposed multiple imputation analysis such that the model cannot converge, or the number of records without missing data is less than the number of records with missing data, the missing HbA1c measurement at Week 16 will be imputed by the patient-level observed baseline value plus a noise, assuming a washout of any potential treatment effect (or “return to baseline”). The noise follows a normal distribution with the variability estimated from the “washout HbA1c data.” The “washout HbA1c data” will be derived by subtracting the corresponding treatment mean at Week 16 from individual non-missing HbA1c values at Week 16.

For non-FDA submissions, the primary efficacy comparison will be based on the contrast between LY900014 and Humalog at Week 16 (Visit 13) from the MMRM analysis of change from baseline in HbA1c including data collected from all randomized patients prior to permanent discontinuation of IP through Week 16 (efficacy estimand). The model for the analysis of the primary efficacy endpoint of change from baseline in HbA1c will include the fixed class effects of treatment, strata (country and patient's personal CGM or FGM use during the study), visit, and treatment-by-visit interaction, as well as the continuous, fixed covariates of baseline value. An unstructured covariance structure will be used to model the within-patient errors. Significance tests will be based on LS means and Type III tests. If this analysis fails to converge, the following covariance structures will be tested in order:

- Toeplitz with heterogeneity

- autoregressive with heterogeneity
- compound symmetry with heterogeneous variances
- Toeplitz
- autoregressive
- compound symmetry without heterogeneous variances

The first covariance structure that converges will be used. The Kenward-Roger approximation will be used to estimate denominator degrees of freedom.

For both primary analysis approaches, LY900014 will be declared noninferior to Humalog if the upper limit of the 2-sided 95% CI for the LS mean difference in the change from baseline in HbA1c for LY900014 minus Humalog is below +0.4%. In addition, the 95% CI for the treatment difference will be compared to an alternative NIM of +0.3%. Both estimands will be tested at the full significance level of 0.05.

In addition to the primary objective, the superiority of LY900014 in controlling HbA1c compared with Humalog will also be assessed for each analysis approach described above. If the p-value is less than the alpha level from the graphical approach allocated to the superiority hypothesis, LY900014 will be declared superior to Humalog.

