
pooled to achieve a pooled country of at least 10 patients. All analyses using country in the model will use a pooled country, unless otherwise specified. The final pooling by country and geographic region will be finalized prior to data lock.

A graphical approach for multiple comparisons (Bretz et al. 2011) will be used to strongly control the overall Type I error (2-sided alpha level of 0.05) for testing the treatment effect for the primary and multiplicity adjusted objectives.

Baseline is defined as the last nonmissing measurement at or before the randomization visit (Visit 4) unless otherwise specified.

A restricted-maximum-likelihood-based, mixed model repeated measures (MMRM) analysis will be used to analyze continuous longitudinal variables. All the longitudinal observations at each scheduled postbaseline visit will be included in the analysis. The model for the analysis of the primary efficacy endpoint of change from baseline in HbA1c will include the fixed class effects of treatment, strata (pooled country and patient's personal CGM use during the study), visit, and treatment-by-visit interaction, as well as the continuous, fixed covariate of baseline value. For analyses of variables other than HbA1c, the HbA1c stratum ($\leq 7.5\%$, $> 7.5\%$) will be included in the model. An unstructured covariance structure will be used to model the within-patient errors. Significance tests will be based on least-squares (LS) means and Type III tests. SAS PROC MIXED will be used to perform the analysis. If this analysis fails to converge, the following covariance structures will be tested in order:

- Toeplitz with heterogeneity
- Autoregressive with heterogeneity
- Compound symmetry with heterogeneous variances
- Toeplitz
- Autoregressive
- Compound symmetry without heterogeneous variances.

The first covariance structure that converges will be used. The Kenward-Roger approximation will be used to estimate denominator degrees of freedom.

An analysis of covariance (ANCOVA) will also be used to analyze continuous variables collected only at baseline and endpoint. The model will include treatment and strata (pooled country, HbA1c stratum ($\leq 7.5\%$, $> 7.5\%$), and patient's personal CGM use during the study) as fixed effects and baseline as a covariate. Unless otherwise stated, missing endpoints will be imputed using the last-observation-carried-forward (LOCF) approach, using only postbaseline data.

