5.2. Determination of Sample Size

Approximately 420 patients will be randomized in order that approximately 368 patients complete the study through the primary endpoint at Week 16.

[figure not shown]
The primary objective of this study is to test the hypothesis that LY900014 is noninferior to Humalog on glycemic control as measured by change from baseline to Week 16 in HbA1c in patients with T1D when administered in a double-blind manner using CSII with bolus doses delivered 0 to 2 minutes prior to the meal.

Patients will be randomized in a 1:1 ratio to double-blind LY900014 with bolus dose delivered 0 to 2 minutes before meals or double-blind Humalog with bolus doses delivered 0 to 2 minutes before meals. Assuming a noninferiority margin (NIM) of 0.4%, no true difference between treatment groups, and a standard deviation (SD) of 0.88%, 368 completers (184 in each treatment group) will provide at least 99% power to show noninferiority between LY900014 and Humalog in change from baseline to Week 16 in HbA1c using the upper limit of a two-sided 95% confidence interval (CI) (LY900014 – Humalog). Assuming a 12% dropout rate for 16 weeks, approximately 420 patients will need to be randomized. This sample size also has 90% power to show noninferiority between LY900014 and Humalog using a 0.3% NIM at Week 16.

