6.1. General Considerations

Statistical analysis of this study will be the responsibility of Eli Lilly and Company (hereafter Lilly) or its designee. Any change to the data analysis methods described in the protocol will require an amendment ONLY if it changes a principal feature of the protocol. Any other change to the data analysis methods described in the protocol, and the justification for making the change, will be described in the SAP or the clinical study report (CSR). Additional exploratory analyses of data will be conducted, as deemed appropriate.

For purposes of analysis, the following populations are defined in [Table ITRO 6.1](#).

Table ITRO 6.1. Patient Populations

Population	Description
Entered	All patients who give informed consent.
Enrolled	All patients who receive at least 1 dose of open-label Humalog in the 2-week lead-in period.
Randomized	All patients who are randomly assigned to study treatment at Visit 4. Treatment group will be defined based on the treatment the patients are assigned.
Safety	All randomized patients who receive at least 1 dose of the randomly assigned IP. Treatment group will be defined based on the treatment the patients were assigned.

Abbreviations: IP = investigational product.

Unless otherwise stated, the efficacy analyses will be conducted on the Randomized Population and the safety analyses will be conducted on the Safety Population.

The primary analysis is for the treatment period up through Week 16.

Unless otherwise noted, all tests of treatment effects will be conducted at a 2-sided alpha level of 0.05, and CIs will be calculated at 95%, 2-sided. All tests of interactions between treatment groups and other factors will be conducted at a 2-sided alpha level of 0.10.

The definitions of baseline and post-baseline for the efficacy and safety analyses depend on which analysis period is being used. The following analysis periods will be used:

- Lead-in Period – Visits 2 to 4
- 16-Week Treatment Period – from randomization to Week 16 prior to discontinuation of IP and from randomization to Week 16 (including all data regardless of IP use)
- 16-Week Treatment Period and Safety Follow-Up Visit – from randomization to Visit 801 (including all data regardless of IP use)

The data on IP is defined based on the following rules:

- For data only measured at an office visit
 - MMTT postbaseline data will be classified as on IP if the MMTT performance date is prior to or on the last IP dose date

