- actual and change from baseline in fasting glucose (average of measurements at time -15 and 0), and PPG at 15, 30, 60, 120, 180, and 240 minutes after the meal
- PPG excursions at time 15, 30, 180, and 240 minutes after the meal (PPG minus fasting glucose)

Sensitivity analysis for PPG and excursions may be performed to exclude patients whose PPG and excursion could be affected by factors including MMTT consumption amount (for example, partial MMTT was consumed).

Treatment comparisons for the proportion of patients with HbA1c $< 7.0\%$ and $\leq 6.5\%$ will be analyzed using a longitudinal logistic regression with repeated measurements conducted by a generalized linear mixed model including independent variables of treatment, baseline HbA1c value, visit, baseline HbA1c-by-visit interaction, and treatment-by-visit interaction. An unstructured covariance structure will be used.

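### The efficacy-estimand primary MMRM fits one baseline HbA1c slope to Weeks 4, 8 and 16; if slopes differ by visit, the Week 16 contrast is mis-adjusted, at a small cost in precision

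*SAP*

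**What the plan says.** SAP 6.11.1 gives two primary analyses. For non-FDA submissions (efficacy estimand) it is an MMRM of change in HbA1c with treatment, country, personal CGM/FGM use, "visit, and treatment-by-visit interaction, as well as the continuous, fixed covariates of baseline value". Protocol 10.3.1 has the same structure: "visit, and treatment-by-visit interaction, as well as the continuous, fixed covariate of baseline value". Neither lists baseline-by-visit. The covariance is unstructured. HbA1c enters at Visits 8, 10 and 13 (SAP Table ITRO 6.2), which are Weeks 4, 8 and 16 in the Schedule of Activities. SAP 6.2 leaves the HbA1c stratum out of this model because continuous baseline HbA1c takes its place.

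Two other HbA1c analyses treat baseline differently, and no reason is given:

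- The longitudinal logistic model for HbA1c targets, over the same visits, includes "baseline HbA1c-by-visit interaction, and treatment-by-visit interaction" (SAP 6.11.4; also protocol 10.3.3.2).
- The FDA primary analysis (ITT estimand, SAP 6.11.1) is an ANCOVA at Week 16 alone, so its baseline slope is specific to Week 16.

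**The concern.** With only a main effect for baseline, the model assumes that change in HbA1c depends on baseline equally at Weeks 4, 8 and 16. If it does not, generalised least squares settles on a compromise slope weighted toward the visits with least residual variance, usually the early ones. The Week 16 contrast is then adjusted with the wrong slope. An unstructured covariance does not correct this, because the error is in the mean model.

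That contrast carries the 0.4% noninferiority test, the comparison with the 0.3% margin, and the H4 superiority test, all for the efficacy estimand. At stake are some precision and, if dropout depends on baseline differently in the two arms, the consistency under missing-at-random data that SAP 6.3 claims for the MMRM. That claim also needs a correct mean model.

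**Working it through.** **1. The plan's own figures.** Inputs from SAP 5.2: "Assuming a noninferiority margin (NIM) of 0.4%, no true difference between treatment groups, and a standard deviation (SD) of 0.88%, 368 completers" (184 per arm). SAP 6.1 sets the level: "all tests of treatment effects will be conducted at a 2-sided alpha level of 0.05".

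- SE = 0.88 × √(2/184) = 0.0917.
- Power = Φ(margin/SE − 1.96).
- Margin 0.4: Φ(4.36 − 1.96) = 99.2%. The plan states "will provide at least 99% power to show noninferiority between LY900014 and Humalog".
- Margin 0.3: Φ(3.27 − 1.96) = 90.5%. The plan states "This sample size also has 90% power to show noninferiority between LY900014 and Humalog using a 0.3% NIM at Week 16".

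Both reproduce.

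**2. Where the common slope lands.** Let b be the vector of visit slopes and S the residual covariance. The fitted common slope is b_c = (1′S⁻¹b)/(1′S⁻¹1). The documents give neither b nor S. Assumed: residual SDs of 0.55, 0.75 and 1.0 times 0.88 (0.484, 0.660, 0.880), and correlation 0.7 between adjacent visits (0.7² = 0.49 for Weeks 4 and 16). The weights on Weeks 4, 8 and 16 are then 0.95, 0.01 and 0.04.

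**3. Effect on the Week 16 standard error.** The Week 16 residual variance becomes 0.88² + (b16 − b_c)² × SDx², where SDx is the baseline SD. Example with slopes −0.15/−0.25/−0.35 and SDx 0.65: b_c = −0.1425 − 0.0025 − 0.014 = −0.159; gap 0.191; SD = √(0.7744 + 0.0154) = 0.889, an increase of 1.0%. In full, with SDx 0.65:

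| Slopes, Weeks 4/8/16 | Gap | SE increase | Power, 0.4 | Power, 0.3 |
|---|---|---|---|---|
| −0.30/−0.30/−0.30 | 0 | 0% | 99.2% | 90.5% |
| −0.20/−0.25/−0.30 | 0.096 | 0.25% | 99.2% | 90.4% |
| −0.15/−0.25/−0.35 | 0.191 | 1.0% | 99.1% | 89.9% |
| −0.10/−0.20/−0.45 | 0.335 | 3.0% | 98.8% | 88.8% |
| −0.05/−0.20/−0.50 | 0.431 | 4.9% | 98.6% | 87.6% |
| −0.40/−0.30/−0.25 (shallower at Week 16) | 0.143 | 0.6% | 99.1% | 90.2% |

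With SDx 0.7 the fourth row becomes 3.5%. The worst setting tried was SDx 0.8 with slopes −0.05/−0.20/−0.50: SD 0.945, SE up 7.4%, power 98.2% and 86.1%.

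**4. Simulation check** (500 runs per setting, models with and without baseline-by-visit). With slopes −0.05/−0.20/−0.50, SDx 0.65, complete data and unstratified randomization, the mean model SE rose from 0.0917 to 0.0962. Power fell from 98.6% to 97.8% at margin 0.4 and from 92.0% to 87.6% at margin 0.3. With randomization stratified on HbA1c, the model SE rose from 0.0917 to 0.0964, but the actual spread of the estimate moved only from 0.0897 to 0.0912. There the loss is mostly an overstated SE. With dropout unrelated to arm, mean estimates stayed within 0.006 of zero and the common slope did not raise the noninferiority error rate. Monte Carlo error is about 0.5 points near 99% power and 1.5 points near 90%.

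**5. Dropout that differs by arm.** A very large fit (N = 200,000, true difference 0, SDx 0.7, about 12% dropout) made dropout depend on baseline in opposite directions in the two arms, which is deliberately adverse. Week 16 contrasts were:

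| Slopes | Common slope | With baseline-by-visit |
|---|---|---|
| −0.15/−0.25/−0.35 | 0.031 | 0.007 |
| −0.15/−0.25/−0.40 | 0.030 | 0.001 |
| −0.05/−0.20/−0.50 | 0.057 | 0.004 |

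Monte Carlo error is about 0.004. When dropout depended on baseline equally in both arms, no bias appeared.

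**6. The other reading of 0.88.** SAP 5.2 does not say whether 0.88 is the residual SD or the unadjusted SD of change. If unadjusted, the common-slope model kept at least 99.2% and 90.8% power in every setting tried, so the planned power is met either way.

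**The case against.** The strongest reply is that the model is prespecified identically in protocol and SAP, that nothing in the documents shows slopes differing by visit, and that no plausible setting changes the 0.4% decision. Randomization is stratified on screening HbA1c (SAP 5.3), which limits the chance imbalance that a wrong slope would leave uncorrected. The logistic model concerns a binary target, where baseline largely determines who falls below a fixed cut-off, so its extra term does not contradict the MMRM.

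Most of this stands. The harm is conditional, the primary test is safe, and the difference between the models is an unexplained inconsistency, not an error. What does not fall away is that the restriction has no stated purpose, brings almost no gain if true, and costs precision if false. Stratification protects the estimate more than it protects its reported standard error (step 4).

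A reader might infer that the model definitely under-adjusts Week 16. The documents do not support that: the direction depends on slopes they do not report. A reader might also assume a smaller Week 16 residual SD, such as 0.60, and arrive at SE increases of 0.6%, 3.6% and 7% in simulation (SDx 0.7). Carrying the same added variance to the plan's 0.88 reduces these to about 0.3%, 1.7% and 3.3%; for example, 0.36 × (1.036² − 1) = 0.0264, and √(1 + 0.0264/0.7744) = 1.017.

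**Conclusion.** The concern holds as a minor, conditional point about efficiency and consistency, confined to the efficacy-estimand MMRM. With 0.88 as residual SD and an assumed baseline SD of 0.65 to 0.7, the Week 16 model SE rises by about 0.3% to 3% for modest to marked slope differences, and by 5% to 7% in extreme ones. Power at the 0.4% margin stays at about 98% or more. Power at the 0.3% margin could fall from 90.5% to about 90% to 87% (86.1% in the most extreme case). H4 for the efficacy estimand uses the same contrast and bears the same SE increase.

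Three stronger readings are not supported. The primary noninferiority conclusion is not at risk from this choice. The contrast is not shown to be biased: bias appeared only under adverse, arm-dependent dropout, reached at most 0.057 against a 0.4 margin, and takes its sign from the dropout pattern. Nor are both primary analyses affected: the FDA ANCOVA, and H4 under the ITT estimand, already use a Week 16 slope.

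All sizes rest on the assumed slopes, baseline SD, residual SDs and correlation.

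**What to change.** Before unblinding, add baseline HbA1c-by-visit to the HbA1c MMRM in SAP 6.11.1. This matches the longitudinal logistic model in SAP 6.11.4 and the Week 16-specific slope of the ANCOVA. It costs two parameters with about 368 completers.

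Because protocol 10.3.1 also states the model, record the departure and its justification in the SAP. Under protocol 10.3.1 and SAP 6.1, an amendment is needed only if the change is judged to alter a principal feature. The sizes above concern HbA1c only; whether to extend the term to the CGM and other MMRMs modelled on this one is a separate decision.
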